4. ANALYSIS SETS

Four (4) analysis sets will be used for the analyses: Full Analysis Set, Per Protocol population, Safety Population and PK/PD Population. Analyses planned for the PK/PD Population will be documented separately.

4.1 Analysis Population Descriptions

4.1.1 Full Analysis Set

The Full Analysis Set (FAS) consists of all participants enrolled and randomised into the study. The FAS population will be used for summaries of participant disposition, demographic and baseline characteristics. Participants will be analysed according to the treatment group they were assigned at randomisation.

4.1.2 Per Protocol population

A per-protocol (PP) population will be based on duration of IMP treatment and protocol deviations. This population may exclude participants with inadequate exposure to IMP or who have other protocol deviations. The PP population is the primary population to analyse efficacy endpoints. Demographic and baseline characteristics of the PP population will also be presented.

4.1.3 Safety population

The safety population consists of all randomised participants who received at least one dose of IMP and had at least one post dose safety assessment. The safety population will be used for the analysis of safety and tolerability. Participants will be analysed as treated, regardless of the randomised treatment assigned, if this differs from that to which the participant was randomised.

4.1.4 PK and PD population

The PK and PD population will include all participants who received at least one dose of IMP, had at least one post dose sample collection for PK and PD analysis and who did not have any clinically significant events or major protocol deviations that may have compromised the integrity of the PK and PD results.

5. PROTOCOL DEVIATIONS

Analysis Set: FAS

All protocol deviations will be listed, grouped by participant and treatment group.

The protocol deviation summary table will include:

- The total number of minor protocol deviations
- The total number of major protocol deviations
- The number of participants who reported at least one minor protocol deviation
- The number of participants who reported at least one major protocol deviation

6. SUBJECT DISPOSITION

Analysis Set: FAS

6.1 General Subject Disposition

A listing of subject disposition will present:

- Date of informed consent
- Date of randomization
- Date of first treatment
- Date of last treatment
- Date of completion / early withdrawal
- Primary reason for early withdrawal

The number and percentage of subjects entering and discontinuing the study will be summarised along with the reason for discontinuation.

The subject disposition summary table will include:

- Number of subjects who received at least one dose of study medication
- Number of subjects who completed the full study
- Number of subjects withdrawn early
- Reason for early withdrawal

6.2 Death

Death related details will be listed only if required.

7. DEMOGRAPHIC AND BASELINE CHARACTERISTICS

Analysis Set: FAS

7.1 Demographics

7.1.1 Parameters

- Date of birth
- Age (years)
- Sex (male/female)
- BMI
- Race
- Ethnicity
- Child-bearing potential
- Menopausal status
- Smoking Habits

7.1.2 Biostatistical methods

Demographic data, inclusive of but not restricted to that listed in 7.1.1 above, will be listed for each participant and summarized using descriptive statistics, tabulated overall for Part A and by treatment sequence and overall for Part B.

7.2 Medical history

All medical history data will be listed.

Medical history (other than disease under study) will be coded using the Medical Dictionary for Regulatory Activities (MedDRA®) and summarised by system organ class (SOC) and preferred term (PT).

7.3 Lumbar Radicular Pain History

All lumbar radicular pain history will be listed for each participant by treatment sequence for Part B only.

7.4 Pregnancy Test

Pregnancy test data will be listed for positive results only.

7.5 Eligibility

All eligibility data will be listed.

7.6 Urine Drug and Alcohol Breath Test

Any positive urine drug screen and alcohol screen tests will be listed.

7.7 SARS-CoV-2 Screening

Any positive SARS-CoV2 screening results will be listed.

8. TREATMENT EXPOSURE

Analysis Set: Safety Population

8.1.1 Parameters

- Date of drug infusion
- Start time of infusion
- End time of infusion
- Date/Time of last meal
- Study drug dose (mg)
- Total volume to be infused (mL)
- Actual volume infused (mL)

8.1.2 Biostatistical methods

All study drug administration data will be listed.

Extent of exposure to LAT8881 and placebo will be summarised for Part A and B as:

- Total IMP administered (mg): Sum of all doses (mg)
- Total Number of participants exposed to study treatment: Sum of all participants treated with LAT8881
- Duration of exposure (hours): (Date / Time last treatment – Date / Time of first treatment) + 1

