#### 21.3.1. Extent of exposure

The number of participants exposed to study treatment, duration of exposure and total IMP administered, will be summarised for Part A and for Part B.

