2. PROJECT OVERVIEW

2.1 Study Design

This is a Proof-of-Concept study that consists of two parts

2.1.1 *Part A (single ascending dose study)*

Part A will be a double-blind, randomized, placebo-controlled, single ascending dose (SAD) study within 8 healthy volunteers of intravenous administration of LAT8881 over 5 minutes.

The SAD study will enrol 8 participants and each participant will have three treatment days, 1 infusion per dosing day on days 1, 4 and 7 as well as two short visits for safety blood sampling on

[figure not shown]
Day 3 and 6 (Figure 1). The 8 participants will be split into two groups of 4 participants each (3 IMP and 1 placebo), with the two groups dosed a few days apart.

Participants will arrive on the morning of each treatment day, receive a single infusion, leave that afternoon (no overnight stay). Participants on a given dosing day will be dosed at staggered intervals as determined by PI.

Treatments will be on Days 1 (0.8 mg/kg), Day 4 (1.2 mg/kg) and Day 7 (1.8 mg/kg) or placebo to allow sufficient washout and consideration of any safety observed following each dosing day. Day 3 and 6 safety blood results will be reviewed prior dosing on the following dosing day.

Participants will fast for 8 hours pre-dose and 4 hours post dose for each dosing occasion. Participants will be randomised, so on each treatment day per group, 3 participants receive LAT8881 and 1 receive placebo (different participants to receive placebo each treatment day). Participants will remain at the clinic until 6 hours post-infusion in order to collect blood samples for PK analysis and for review of safety and tolerability. Safety assessments will be reviewed in a clinic exit visit 7 days after the last infusion.

Figure 1: Part A Study Design

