2.1.2 Part B (Cross-Over Study)

Part B will be a placebo-controlled randomized double blind cross-over safety and efficacy study of LAT8881. Up to 20 participants will be randomized into two groups and will receive either a single dose of LAT8881 [the dose selected from Part A of the study] or placebo via intravenous administration over 10 minutes on two consecutive days.

Participants will be randomly assigned to one of two groups, active then placebo or placebo then active (Figure 2).

After passing screening, participants will be admitted for two nights:

1. A study staff member will contact the participant for 3 consecutive days to obtain a verbal pain score out of 10 to confirm that their mean resting radicular pain meets the study inclusion criteria (pain score on each of the 3 days must be ≥ 3)
2. The participant will arrive the evening prior to dosing, and will complete a final review of inclusion/exclusion criteria.
3. Baseline assessments will be completed on the first day of dosing prior to IMP administration
4. The participant will then receive their first dose.
5. Collection of blood samples for PK/ PD analysis and assessments for review of safety, tolerability and efficacy are listed in the Schedule of Assessments.

The participants will stay overnight.

If the PK from the Part A demonstrates elimination in <6 hours (assessed by concentration below LOQ of assay),

[figure not shown]
6. The following morning the participants will cross-over and receive their second dose.
7. Collection of blood samples for PK analysis and assessments for review of safety, tolerability and efficacy are listed in the Schedule of Assessments.
8. Participants will remain at the clinic until 6 hours post the second infusion and then may be discharged.

At the discretion of the Investigator and in consultation with the Study Sponsor, the requirement for subjects to be admitted to the clinic from the evening before Day 1 through to discharge at the end of Day 2 can be waived. In such circumstances, items 1 through 8 above will still apply, with the following modification to item #2:

- During the morning of Day 1 the following will be undertaken prior to dosing: a) a complete final review of inclusion/exclusion criteria, b) a written account of the activities the participant undertook on Day 0.
- Prior to dosing on Day 2, a written account of the activities the participant undertook after discharge at the end of Day 1.

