3.2.3 Study Day

Part A: Study Day will be derived as the number of days relative to date of first administration of study drug, where the day of first administration = 1.

Part B: Study Day will be number of days relative to date of administration of study drug for each period, where the day of administration = 1.

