3.2.5 Treatment groups – Part A

Tabulations will summarize data by treatment group, the pooling of all the study drug, and total (all groups). All placebo participants will be grouped in a single cohort for tabulation summaries.

For Part A, treatment groups within tables are planned to be presented as:

LAT8881 (0.8mg/kg) (N=X)	LAT8881 (1.2mg/kg) (N=X)	LAT8881 (1.8mg/kg) (N=X)	LAT8881 (All Doses) (N=X)	Placebo (N=X)	Total (N=X)
--------------------------------	--------------------------------	--------------------------------	---------------------------------	------------------	----------------

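### SAP 8.1.2 adds 1 to an interval measured in hours, so the duration-of-exposure row is neither a correct dosing span nor a measure of LAT8881 exposure

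*SAP*

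**What the plan says.** Protocol section 21.3.1 requires that "duration of exposure and total IMP administered, will be summarised for Part A and for Part B". It gives no formula and does not define the term.

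SAP section 8.1.2 supplies the derivation: "Duration of exposure (hours): (Date / Time last treatment – Date / Time of first treatment) + 1". It does not explain the added 1, and it does not say whether the date/time of a treatment is the start or the end of the infusion. No other section redefines the variable.

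The dosing pattern comes from SAP section 2.1. In Part A, "each participant will have three treatment days, 1 infusion per dosing day on days 1, 4 and 7", each infusion lasting 5 minutes. In Part B, participants receive LAT8881 or "placebo via intravenous administration over 10 minutes on two consecutive days", then cross over.

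The inputs for an infusion-level measure are already in SAP section 8.1.1. Besides the start time, it lists "End time of infusion" and "Actual volume infused (mL)", together with the volume that was meant to be given.

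On layout, SAP section 3.2.5 says for Part A: "Tabulations will summarize data by treatment group, the pooling of all the study drug, and total (all groups)". SAP section 3.2.6 puts Part B exposure by treatment sequence and total, not by treatment received.

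**The concern.** A first-to-last difference plus 1 is the usual way to count days inclusively. SAP section 3.2.3 numbers days in that spirit for Part A, as "the number of days relative to date of first administration of study drug, where the day of first administration = 1". The variable in 8.1.2 is labelled in hours, where an added 1 is simply an extra hour. It looks like a day-count convention carried over to an hours variable. That origin is an inference, since the SAP does not state it, but the error does not depend on it.

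There is a second difficulty. Treatment here is two or three short, isolated infusions, so the time from first to last dose is almost entirely time off drug. In Part B one of the two infusions is placebo, so the interval does not describe LAT8881 exposure.

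At stake is one row of a safety table that the protocol requires. Programmed as written, the row would carry a wrong number under a label that a reader could take for time on drug.

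**Working it through.** The documents state no exposure value, so there is no figure of the plan's own to reproduce. The check applies the 8.1.2 formula to the planned schedule.

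**Inputs**
- Part B: two infusions of 10 minutes on consecutive days (SAP 2.1.2).
- Part A: three infusions of 5 minutes on Days 1, 4 and 7 (SAP 2.1.1). On each day one of the four participants in a group receives placebo, a different one each time. Three of the four therefore have two active infusions and one has three.
- Assumption: the same clock time on each dosing day for a given participant, with treatment time taken as the start of infusion.

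**Formula applied to the whole participant**

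| | First-to-last span | SAP result (span + 1) | Excess as a span | Planned infusion time |
|---|---|---|---|---|
| Part B completer | 1 × 24 = 24 h | 25 h | 1/24 = 4.2% | 2 × 10 = 20 min, of which 10 min LAT8881 |
| Part A completer | 6 × 24 = 144 h | 145 h | 1/144 = 0.7% | 3 × 5 = 15 min, of which 10 or 15 min LAT8881 |
| Dosed once, either part | 0 h | 1 h | 1 h on a span of 0 | 5 or 10 min |

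**Sensitivity to the assumptions**
- If the clock time of the last dose shifts by up to 3 h either way (an assumed range), the SAP result is 22 to 28 h in Part B and 142 to 148 h in Part A. The extra hour is present throughout.
- If the interval runs from the start of the first infusion to the end of the last, the results are 24 + 10/60 + 1 = 25.17 h and 144 + 5/60 + 1 = 145.08 h.

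**Does the + 1 fit another unit?** In days it does: 2 − 1 + 1 = 2 days for Part B and 7 − 1 + 1 = 7 days for Part A. Those equal 48 h and 168 h, which the formula does not return and the label does not describe.

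**Part A by table column.** The SAP does not say whether first and last treatment are found across all treatments or within each column. If within column, on a start-to-start reading:
- each single-dose column gives 0 + 1 = 1 h for every participant;
- the column pooling all LAT8881 doses gives 72 + 1 = 73 h where placebo fell on Day 1 or Day 7, and 145 h where it fell on Day 4 or on no day.

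On that reading the single-dose columns carry no information, and the pooled column varies with the placebo day.

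**The case against.** The strongest reply is that the SAP may define duration of exposure as a dosing span. The protocol asks for a duration without saying that it means infusion time. On that definition the indisputable error is 1 h, which in Part B is smaller than plausible variation in dosing times. Much of this stands. It means that the gap between 25 h and 20 minutes, or between 145 h and 15 minutes, should not be reported as a multiple by which exposure is overstated. Such a multiple measures distance from a preferred definition that the documents never set. The reply does not rescue the + 1, and it does not turn a Part B span from active to placebo, or the reverse, into LAT8881 exposure.

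It can also be said that the SAP already has a row for total mg administered, lists all administration data, and collects planned and actual volumes, so a duration row need not reveal a partial dose. That is fair, and it is one reason why the point is minor.

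Two stronger readings are tempting, and the documents support neither:
- **That the formula distorts the per-protocol population.** SAP section 4.1.2 does base that population partly on how long treatment lasted, but it does not link this to the 8.1.2 row. The absence of detailed per-protocol rules is a separate matter and would remain if 8.1.2 were perfect.
- **That the formula hides the two participants who received an estimated 60-65% of the dose.** SAP section 2.5 attributes this to problems with the infusion equipment. It does not say whether infusions stopped early or ran slowly, so the effect on any duration measure cannot be worked out from the documents.

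**Conclusion.** The derivation is wrong as written, and the point is minor. If a span in hours was meant, the row is 1 h too long for everyone. If a day count was meant, the unit is wrong. If time on drug was meant, the formula measures something else. The size, at equal clock times and start to start, is about 25 h in Part B against a span of 24 h, 145 h in Part A against 144 h, and 1 h for anyone dosed once. The Part A figure applies to the whole participant; single-dose columns computed within column would show 1 h. The Part B span mixes active and placebo infusions because of the by-sequence layout.

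Nothing beyond this row is affected. It is descriptive, it feeds no efficacy estimate, and the listed administration data would let a reader see and correct the error.

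**What to change.** - In SAP 8.1.2, drop the + 1 and derive duration for each infusion as end time minus start time, in minutes, from the fields in 8.1.1.
- Summarise this row by treatment received, and by dose in Part A. For Part B this also means amending the line in SAP 3.2.6 that sets exposure out by sequence.
- If a first-to-last dosing span is also wanted, give it its own labelled row, either in days with the + 1 or in hours without it, and state whether it uses infusion start or end times.
- Optionally, add the ratio of actual volume infused to total volume to be infused, since a duration row may not show a partial dose.

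The cost is a revised derivation, a matching change to the table layout and a few lines of SAP wording. No new data are needed. If the SAP is already final, its section 14 provides for describing and justifying the change in the final report.

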9. PHARMACOKINETICS

Analysis Set: PK Population

Refer to PK Analysis Plan

All results of pharmacokinetic assays will be reported in listings.

10. PHARMACODYNAMICS

Refer to PD Analysis Plan.

11. EFFICACY (PART B ONLY)

Analysis Set: Full Analysis Set and Per Protocol population

Parameters:

- Pain now VAS score:
 - Change from Baseline to hours 0.25, 0.5, 0.75, 1, 1.5, 2, 2.5, 3, 3.5, 4, 5 and 6,
 - Percentage change from baseline to hours 0.25, 0.5, 0.75, 1, 1.5, 2, 2.5, 3, 3.5, 4, 5 and 6
 - Peak change from baseline over 6 hours
 - Mean change from baseline over 1 to 2 hours
 - Mean change from baseline over 5 to 6 hours
- Pain on leg raise VAS score:
 - Change from Baseline to hours 0.25, 0.5, 0.75, 1, 1.5, 2, 2.5, 3, 3.5, 4, 5 and 6,
 - Percentage change from baseline to hours 0.25, 0.5, 0.75, 1, 1.5, 2, 2.5, 3, 3.5, 4, 5 and 6

- Peak change from baseline over 6 hours
 - Mean change from baseline over 1 to 2 hours
 - Mean change from baseline over 5 to 6 hours
- Patients general impression of change at hour 6 on Day 1 and on Day 2
- Mechanical QST assessment using Von Frey Aesthesiometer
- Bang Binding Index assessment at 6 hours on Day 2

11.1.1 Biostatistical methods

Efficacy will be assessed based on the difference between treatments in the following measures:

Pain Now Scores (VAS)

“Pain now” scores, change from baseline, percentage change from baseline and summary scores (i.e. maximum change from baseline, mean change from baseline over 1 to 2 hours and mean change from baseline over 4 to 6 hours) will be listed for all study participants at each timepoint by treatment sequence.

Descriptive statistics including the number of participants, mean, standard deviation, median, minimum and maximum for the VAS “pain now” score at each timepoint along with the change from baseline and percentage change from baseline will be presented by treatment group within treatment period and overall. The mean, standard deviation, median, minimum and maximum for the change from baseline over 6 hours, the mean change from baseline over 1 to 2 hours and the mean change from baseline from 4 to 6 hours will be presented by treatment group within treatment period and overall.

Graphical presentations will include those presented for the interim analysis:

1. Individual subject VAS scores-time profiles by timepoint and by sequence (left panel LAT8881-Placebo, right panel Placebo-LAT8881)
2. Group mean VAS scores by timepoint and day, two sequences combined (one panel only)
3. Group mean VAS scores by timepoint and day in each panel, and by sequence (left panel LAT8881-Placebo, right panel Placebo-LAT8881)

Additional graphical presentations will include:

4. Individual subject change from baseline -time profiles by post-dose timepoint and by sequence (left panel LAT8881-Placebo, right panel Placebo-LAT8881)
5. Group mean change from baseline by post-dose timepoint by treatment, two sequences combined (one panel only)
6. Group mean change from baseline by post-dose timepoint and by sequence (left panel LAT8881-Placebo, right panel Placebo-LAT8881)
7. Difference between treatments in the change from baseline at each post-dose timepoint by sequence (left panel LAT8881-Placebo, right panel Placebo-LAT8881)
8. Difference between treatments in the change from baseline at each post-dose timepoint by treatment (one panel only)
9. A scatter plot for baseline scores with Placebo score on the x-axis, LAT8881 score on the y-axis, a diagonal line with slope=1 representing no difference between treatments will be overlaid on the plot, symbols and symbol colour will be used to identify treatment sequence.
10. Maximum change from baseline will be presented using the same scatter plot format as for baseline scores
11. Mean change from baseline over 1 to 2 hours will be presented using the same scatter plot format as for baseline scores
12. Mean change from baseline over 5 to 6 hours will be presented using the same scatter plot format as for baseline scores

To estimate the difference between LAT8881 and Placebo in the change from baseline "pain now" VAS over all session time points, a generalised linear mixed effects model will be fitted. Fixed-effects will include treatment, session time point and period (i.e. Day) factors; baseline will be included as a covariate. Random effects for participants and participant by period will be included to take into account the repeated measures on each participant and the cross-over nature of the study. The covariance structure for the random effects is assumed to follow a compound symmetry structure. The estimated adjusted (least squares) mean change from baseline for each treatment at each session time, the difference between the treatments, the 95% confidence interval for the difference and the p value for the difference will be presented. A p value of <0.05 will be declared statistically significant. The model assumes no carry-over treatment effect and assumes that any period (i.e Day) effect will affect subjects in both treatment sequences in a similar manner.

The same model will be fitted to the change from baseline "pain on leg raise" VAS scores. As reflected in the scientific literature and regulatory authority guidelines, what constitutes a minimally significant change in baseline pain score can vary from subject-to-subject, whether the pain is acute or chronic, and on the mechanism of the pain. For the purposes of this study, the sponsor considers a 0.9 cm reduction to represent a minimally clinically significant change in pain as reported on the VAS, with the desired target reduction from baseline in the range of 0.9 to 3 cm.

Provocation Assessment with VAS

The pain on leg raise VAS score, change from baseline, percentage change from baseline, maximum change from baseline, mean change from baseline from 1 to 2 hours and mean change from baseline from 4 to 6 hours will be listed for all study participants at each timepoint by treatment sequence as for the "pain now" endpoints. Descriptive summary tables and analyses will be as per the "pain now" endpoints.

Patients general impression of change

The assessment responses will be listed for all participants by treatment sequence and visit.

The number and percentage of participants in each rating category will be summarised by treatment within period (i.e. Day) and overall.

A graphical presentation will take the form of a heat map with the rating categories for Placebo on the x-axis and the rating categories for LAT8881 on the y-axis. Each cell will contain the percentage of subjects with the corresponding combination of PGIC and will be colour-coded to represent the weight of evidence for the corresponding percentage.

The categories of general impression of change:

- Very much improved
- Much improved
- Slightly improved
- No change
- Slightly worse
- Much worse
- Very much worse

Quantitative Sensory Test (QST) assessment

The Affected and Non-affected dermatome monofilament pain assessment data will be listed for all study participants at each timepoint by treatment sequence.

The number and percentage of participants with pain at each filament will be summarised by type of dermatome and treatment sequence at each timepoint with the number of subjects, mean, standard deviation, median, minimum and maximum by treatment group within treatment period and overall.

Bang Binding Index assessment

The Bang Binding Index assessment identifying which Day the subject believed they were treated with the active treatment will be listed for all study participants.

The number and percentage of participants who correctly identified when they were using active treatment will be presented by treatment sequence and overall.

Sub-group Assessment of Demographic Factors

The contribution of demographic factors (listed in 7.1.1 above) to any differences in efficacy between treatment groups will be investigated.

